6.0 Statistical Methods and Data Analysis

Ratings of pain will be measured by visual analog scales for pain as well as unpleasantness of pain sensation (i.e. “how much pain are you in right now?” and “how much is the pain bothering you right now?”). Patient reports of sensory and pain detection using the Quantitative sensory testing (QST) with the Medoc device will also be used, with and without stimulation.

In Phase 2, patients will serve as their own controls in a single-blinded phase (6-months in duration) in which placebo versus active open-loop stimulation is used. During this 6-month period, four sham and four active stimulation periods will occur in a random, blinded assignment. During the 8 in-clinic visits, the threshold for sensory and pain detection with the Medoc device will be used and scores will be compared for each patient during sham versus active stimulation periods in one-sample, two-tailed t-test. The 10 patients’ sham versus stimulation scores will also be used in group analysis to test the effects of open-loop and closed-loop stimulation.

In Phase 2, the visual analog scale scores recorded during the at-home recording sessions for various activities will be compared for each patient [(see Figure 3; 168 scores for sham sessions and 168 scores for active stimulation sessions, per patient); (i.e. 3 times per week for 4 activities and 2 times per week for at least 1 painful activity, for at least 14 VAS scores per week; 24 weeks total with 3 weeks per session-sham or stimulation, 8 sessions total, 4 sham sessions and 4 stimulation sessions)].

Multiple regression analysis of all patients will also be used to test for effects of stimulation on various activities, time of day, stimulation effects over time in trial and potential differences in stimulation effects on pain etiologies (i.e. spinal cord injury versus phantom limb versus post-stroke).

Phase 1 (no-intervention) VAS scores will be compared to Phase 2 (sham controlled and active stimulation) VAS scores.

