In Phase 3, patients will serve as their own controls in a single-blinded phase (12-months in duration) in which closed-loop versus active open-loop stimulation is used. During this 12-month period, ~four sham and ~four active stimulation periods will occur in a random, blinded assignment. During the ~8-9 in-clinic visits, the threshold for sensory and pain detection with the Medoc device will be used and scores will be compared for each patient during sham versus active stimulation periods in one-sample, two-tailed t-test. The 10 patients’ sham versus stimulation scores will also be used in group analysis to test the effects of open-loop and closed-loop stimulation.

In Phase 3, the visual analog scale scores recorded during the at-home recording sessions for various activities will be compared for each patient [(see Figure 3; ~364 scores for sham sessions and ~364 scores for active stimulation sessions, per patient); (i.e. ~3 times per week for 4 activities and 2 times per week for at least 1 painful activity, for at least ~14 VAS scores per week; ~52 weeks total with 6 weeks per session-sham or stimulation, ~8 sessions total, 4 sham sessions and 4 stimulation sessions)].

Multiple regression analysis of all patients will also be used to test for effects of stimulation on various activities, time of day, stimulation effects over time in trial and potential differences in stimulation effects on pain etiologies (i.e. spinal cord injury versus phantom limb versus post-stroke).

Phase 1 (no-intervention) and Phase 2 (sham controlled and open-loop stimulation) VAS scores will be compared to Phase 3 (open-loop stimulation and closed-loop) VAS scores.

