LFP data will be analyzed using wide spectrum power-spectral analysis as well as using specific frequency domain for mean log power (i.e. in the delta, theta, alpha, beta, gamma bands). We will also examine coherence and cross-frequency coupling between the channels [145-147]. Using a repeated measures ANOVA statistical analysis, summary statistics for power in relevant frequency bands, pain-related power changes, and indices of phase-amplitude coupling will be compared at different time points, different DBS conditions (on and off), possible medication states (on and off) and different pain states. Although the sample size is small, we will assess the correlation between pain and non-pain states with brain physiology measures, and clinical instruments used to measure pain relief produced by DBS. Additionally, bootstrapping statistical applications (i.e. a Monte Carlo algorithm) and general linear mixed models can be utilized to investigate potential statistical effects, given the small sample size.

Neural activity will be compared during pain states, activity states, medication states, etc. for Phase 1 (no-intervention), as well as Phase 2 (sham controlled and open-loop stimulation) and Phase 3 (open-loop stimulation and closed-loop stimulation).

Sample size calculation: This is a pilot study consisting of existing chronic brain recording technology. The goals are to provide pain relief strategies using the Activa PC+S neural interface, as well as assess feasibility and to collect data that will be used to inform treatment plans using DBS mechanisms. Thus, there is no formal sample size calculation. However, the study is designed such that patients will serve as their own controls in a blinded, placebo versus active open-loop stimulation design, with multiple periods of placebo versus active stimulation. Patients will also serve as their own controls in open-loop versus closed-loop stimulation, in a randomly assigned, blinded, multiple 6-week time periods of open-loop versus closed-loop stimulation. At-home recording sessions will also be utilized to increase the number of testing samples per patient over the trial. In this manner, the statistical power is increased to show treatment efficacy in either of these phases.

Criteria for study success that would justify a larger subsequent trial: This study will be considered to justify a larger subsequent trial if we can demonstrate that:

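### Home VAS is planned in single scores and a pooled regression naming no patient or period term, although stimulation is randomised by period (about 4 vs 4 per patient)

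*Combined protocol and SAP*

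**What the plan says.** The synopsis lists pain VAS as a primary endpoint without saying where it is recorded. The home scores are the randomised VAS comparison that Section 6.0 describes in detail.

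- **Allocation.** In Phase 2, "four sham and four active stimulation periods will occur in a random, blinded assignment", each lasting three weeks. Phase 3 randomises open-loop or closed-loop in six-week periods (Sections 1.0 and 3.0).
- **Per-patient comparison.** Phase 2 compares "168 scores for sham sessions and 168 scores for active stimulation sessions, per patient", built from a weekly rate stated as "for at least 14 VAS scores per week". Phase 3 compares about "364 scores for sham sessions and ~364 scores for active stimulation sessions, per patient", from about "52 weeks total with 6 weeks per session-sham or stimulation, ~8 sessions total, 4 sham sessions and 4 stimulation sessions". (Section 6.0 keeps the sham and active labels here, although the phase compares open-loop with closed-loop.) No test is named for VAS; the t-test is specified only for QST thresholds.
- **Group analysis.** A multiple regression over all patients tests stimulation effects by activity and time of day, plus "stimulation effects over time in trial and potential differences in stimulation effects on pain etiologies". No patient, patient-by-stimulation or randomised-period term is named.
- **Mixed models.** The paragraph on LFP data says that "general linear mixed models can be utilized to investigate potential statistical effects, given the small sample size". No random effects are given and there is no explicit link to home VAS.
- **Power.** Under the sample size heading: "At-home recording sessions will also be utilized to increase the number of testing samples per patient over the trial". The plan then says that power is thereby increased.

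**The concern.** The unit that is randomised is the period, but the comparison is counted in single scores. Scores within one period share whatever was happening then, such as a flare or a change in a medication regimen managed outside the study. With about four periods per condition, such shifts do not average out within a patient. An analysis that treats scores as independent reads them as evidence about stimulation.

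This matters in two places. Section 3.0 expects Phase 3 to show which stimulation mode works better in each patient, so a misleading individual verdict defeats that phase. The regression also looks for different stimulation effects by pain etiology, and a spurious difference could shape the larger trial that this pilot is meant to justify. The third success criterion asks for demonstrated benefit but names no test, so nothing later in the plan corrects the problem.

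The power statement is partly right: more scores make each period mean more precise. It omits that the gain is capped by about 4 vs 4 periods per patient and by 10 patients.

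**Working it through.** **1. The plan's own counts** (inputs from Section 6.0)

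- Per week: 3 × 4 + 2 × 1 = 14.
- Phase 2: 14 × 3 = 42 per period; 42 × 4 = 168 per condition. This reproduces the stated figure.
- Phase 3: 14 × 52 / 2 = 364 reproduces the stated figure. But four six-week periods give 14 × 6 × 4 = 336 (84 per period), because 8 × 6 = 48 weeks, not 52. 364 / 336 = 1.083, so the stated count is 8% higher.

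**2. Per-patient error if scores are treated as independent**

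Assumed, because the documents give none of these: two-sided 5% level, total within-patient variance 1, and a share ICC of that variance lying between periods. With k = 4 periods per condition, m scores per period and n = km:

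- True variance of the difference: 2 × [ICC/k + (1 − ICC)/n].
- Variance the score-level test uses: 2s²/n, with expected s² = n/(n − 1) × [1 − ICC/k − (1 − ICC)/n].

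Phase 2 at ICC 0.05: true 2 × (0.0125 + 0.00565) = 0.0363; used 2 × 0.988/168 = 0.0118. The ratio is 3.09, its square root 1.76, and 1.96/1.76 = 1.115, giving a false-positive rate of about 26%. The design effect is 1 + 41 × 0.05 = 3.05, so 168 scores carry the information of about 55.

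Simulation (20,000 trials per cell) agrees. False-positive rates at ICC 0.01 / 0.05 / 0.20:

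| Score-level analysis | Phase 2 | Phase 3 (84 per period) |
|---|---|---|
| Independent period effects, random 4 vs 4 | 10 / 26 / 53% | 15 / 39 / 65% |
| Same, plus a linear time term | 10 / 27 / 53% | 15 / 39 / 66% |
| Autocorrelated period effects (0.7), random | 8 / 19 / 42% | 11 / 29 / 56% |
| Autocorrelated (0.7), strict alternation | 6 / 10 / 26% | 7 / 16 / 40% |

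At ICC 0 the rate is 5%. Seven Phase 2 periods (4 vs 3) give 10 / 27 / 54%. A linear time term does cure pure linear drift (Phase 2: 11 / 29 / 57% without it, 5% with it), but not shifts specific to a period. The t-test on period means gives 5–6% under random allocation and is conservative (1–4%) under alternation with autocorrelation.

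**3. Pooled regression with the named terms**

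Assumed: 10 patients, etiologies split 4/3/3, a between-patient share of 0.3 of total variance, and linear time (4,000 trials). Shares here are of total variance, so a period share of 0.05 is a within-patient ICC of 0.05/0.7 = 0.071. Rates at period share 0.02 / 0.05 / 0.10:

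| Test | Phase 2 | Phase 3 |
|---|---|---|
| Stimulation by etiology | 18 / 39 / 57% | 32 / 58 / 75% |
| Stimulation | 13 / 26 / 39% | 23 / 41 / 52% |
| Stimulation by etiology, patient term added, no period term | 25 / 48 / 64% | 42 / 67 / 81% |

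With no period variance the interaction test rejects about 2%. With autocorrelation 0.7 at share 0.05 it rejects 23% (Phase 2) and 41% (Phase 3). A 6/2/2 split gives similar figures (16 / 38 / 57% and 30 / 57 / 74%). Adding a patient term alone makes matters worse, so the period term is the one that counts. Tests on the 10 patient-level differences give 4–6%.

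**4. The cap on power**

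The Phase 2 per-patient difference detectable with 80% power is 0.31 within-patient SD if 168 scores per condition were independent. With 4 vs 4 period means it is 0.64, 0.83 and 1.11 SD at ICC 0.05, 0.10 and 0.20.

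**The case against.** The error is inferred. No VAS test is named, and the bracket that counts scores also lists the eight sessions, so averaging by period is compatible with it. The plan says repeatedly that patients are their own controls, and it mentions a group analysis of the ten patients' sham and stimulation scores. The mixed-model sentence follows one about clinical instruments for pain relief, so it may reach VAS. The power paragraph cites multiple periods as well as home scores. The regression sentence lists effects to test and may not be a full model; time in trial is not said to be linear. Every inflation figure rests on an assumed variance share. This is a ten-patient pilot with no stated alpha.

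Part of this stands. Score-level analysis is what the counts and the power argument suggest, not what the plan declares, and the rates are conditional. A mixed model also needs small-sample degrees of freedom: with 10 patients, a large-sample z test rejected about 8% in one approximation (period share 0.05, 42 scores per period, stimulation effect varying between patients with SD 0.3).

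The rest does not close the gap. Serving as one's own control does not say whether the score or the period is the unit. The group-analysis sentence follows the QST text and specifies no model. The mixed-model sentence is optional and names no random effects. Run with only the terms it names, the regression has the error rates shown.

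**Conclusion.** The concern holds and should be fixed. Section 6.0 leaves the unit of analysis for home VAS open, counts it in scores, and names a pooled model without the period structure on which stimulation is randomised. If scores are treated as independent, a within-period correlation of only 0.01 roughly doubles the per-patient error in Phase 2 (10% against 5%) and triples it in Phase 3 (15%). Larger correlations, and the stimulation-by-etiology test, do worse. There is no inflation at zero period variance, and less with autocorrelated period effects or strict alternation. Confidence is high for the omission; the size depends on variance shares that the documents do not give. The mismatch of about 364 with 336 is minor.

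**What to change.** In Section 6.0:

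- State that the randomised period is the unit for home VAS. State whether allocation is random 4 vs 4 or alternating, because Section 6.0 and the Phase 3 visit list in Section 1.0 can be read either way.
- Per patient: take one mean VAS per period and compare by a t-test on period means, or by a randomisation test over the allocations actually possible.
- Group: use a t-test on the 10 patient-level differences, or a mixed model with patient, patient-by-stimulation and period-within-patient terms and small-sample degrees of freedom, keeping the time, activity and time-of-day terms.
- Report etiology differences descriptively or on patient-level differences.
- Qualify the power sentence: extra scores sharpen each period mean, but power is limited by about 4 vs 4 periods and 10 patients.
- Reconcile 364 with 336, and the 7 Phase 2 visits of the Protocol Chart with the 8 of Section 6.0. Call the totals planned counts: Phase 2 may be shortened, and Section 3.0 describes home collection as optional for the Phase 1 downloads and as something patients may do in Phase 3.

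**Cost.** SAP wording and a little analysis; conduct does not change. Per-patient intervals widen. With 70 allocations at 4 vs 4, the smallest two-sided randomisation p is 2/70 = 0.029 and the next is 0.057, so the test's level is about 3%. For an assumed 0.5 SD effect at ICC 0.05 in Phase 2, its power is 43%, against 59% for the t-test on period means. At 3 vs 3 the smallest p is 2/20 = 0.10. Under strict alternation only two sequences exist, so a randomisation test cannot reject and the period-mean t-test is the option. The group cost is small: for an assumed 0.3 SD effect in Phase 2, the t-test on 10 differences has 100 / 100 / 94% power at period share 0.02 / 0.05 / 0.10, or 73 / 67 / 60% if the effect varies between patients with SD 0.3.

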Study Design	
This is a single-center study of the effectiveness of open- and closed-loop DBS paradigms in the treatment of chronic neuropathic pain disorders that are refractory to current treatment options (e.g. two or more pain medications from different classes, spinal injections).
 
Our primary objectives are to:
 
 1) Determine the neural correlates of increased pain states in patients with chronic pain in order to enable targeted DBS treatment 2) Provide pain relief with neural stimulation 3) Establish the efficacy of open-loop and closed-loop DBS paradigms. 
DBS electrodes will be inserted into regions of the brain related to pain processing. After implantation of electrodes, study patients will undergo three phases of assessment.
 
In phase 1, patients will undergo ambulatory monitoring (~6 months) of their pain states linked to recordings of local field potentials (LFPs) in pain-processing regions. Stimulation will not be enabled during this period. This phase will be conducted in both the outpatient office setting and the patient's home environment. Throughout this period, data will be analyzed to develop a predictive model of increased pain states and to guide precision DBS treatment.
 
In phase 2, we will determine the stimulation parameters that optimally reduce the level of pain for each patient, in clinic daily, for 1-2 weeks. We will then randomly assign patients to 3-week periods of stimulation ON / stimulation OFF. We anticipate this phase will last approximately 6 months and that stimulation will be conducted in the office as well as the home setting. Patients will be under close monitoring, with frequent in-clinic appointments.

	
In phase 3, we will determine differences in pain relief efficacy for at-home open-loop versus closed-loop stimulation parameters (single-blind study). Patients will be under close monitoring, with frequent in-clinic appointments.
 
In phase 1, if data of sufficiently high quality is collected before the 6 month phase period ends, and a predictive biomarker is found before the 6-month phase period ends, the patient can accelerate to the next phases of the study to help ensure a rapid positive clinical outcome. Similarly, the patient may accelerate from phase 2 to phase 3 before the 6-month period ends to ensure rapid positive clinical outcomes.

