14. Visits 25-31: every 3 weeks for closed loop / placebo randomization:

- Clinical: visit 28 only; History and Physical for stability
- Research: visits 25-31: Activa Data collection + QST:
- Quantitative sensory testing (QST) with the Medoc device. Using cold and heat, we will test sensory perception and pain thresholds 3 times each in the aspect of both hands (contra and ipsi lateral to pain). The device will slowly increase/ decrease temperature until the patient reports sensation (1st endpoint) and then pain (2nd endpoint) which will be recorded. Heat and cold perception and pain thresholds will be tested, with the patient record VAS for pain threshold on each trial. Three consecutive trials will be conducted in each session to establish reliability. LFP recordings will be recorded during the QST sessions with clinician initiated recording. LFP recordings will also be recorded during pre-identified painful activities or

movement and after painful activity with VAS scores recorded during these times as well.

- Patients will be asked to avoid pain medication two hours prior to their appointments. Post-testing, patients will then take medications and 2-minutes of recording will be obtained 15-minutes after pain medication is given.
- Baseline LFP recordings will also be taken from ~2 minutes.
- Stimulation off + QST (no pain medication)
- Stimulation on + QST
- Wash-out, stimulation off period
- LFP recording after painful activity
- Recording after pain medication
- C-SSRS/BDI/BAI/ NIH PROMIS /NPQ/physical function scales and SF-36

Phase 2 will last approximately 6 months in duration, time period based on previous unpublished observations in human Parkinson's patients from our group [143] and published non-human primate observations [58], visits 11-34, if needed)

Phase 2 will test the effectiveness of closed-loop stimulation in comparison to no-stimulation.

In phase 3, the effectiveness of closed-loop stimulation will be tested in comparison to open-loop stimulation settings.

Phase 3

In phase 3, patients will continue with at-home stimulation with either personalized closed-loop or traditional open-loop stimulation strategies their implanted system. Patients will be blinded to the stimulation strategy in which they are assigned. Assignment of open-loop or closed-loop will be randomized and occur in 6-week time periods, with each patient serving as his or her control as to which stimulation treatment is more effective.

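### Section 6.0 analyses Phase 3 as sham versus active, but Phase 3 randomises closed-loop versus open-loop, so Hypothesis 3 has no specified test; the Phase 2 active mode is also labelled inconsistently

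*Combined protocol and SAP*

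**What the plan says.** **Phase 3 design.** The synopsis (Study Design) says: "In phase 3, we will determine differences in pain relief efficacy for at-home open-loop versus closed-loop stimulation parameters (single-blind study". Section 3.0, Phase 3, says: "Assignment of open-loop or closed-loop will be randomized and occur in 6-week time periods". Section 1.0, the entry for Visits 32-41, the Nexus System Study text and the sample size paragraph of Section 6.0 agree on randomised, blinded assignment between these two modes. The Protocol Chart also lists open versus closed for this phase.

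**Phase 3 analysis.** The first Phase 3 sentence of Section 6.0 describes a single-blinded year "in which closed-loop versus active open-loop stimulation is used". The labels then change:

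- Periods: "During this 12-month period, ~four sham and ~four active stimulation periods will occur in a random, blinded assignment".
- QST, per patient: "scores will be compared for each patient during sham versus active stimulation periods in one-sample, two-tailed t-test".
- Group analysis: "sham versus stimulation scores will also be used in group analysis to test the effects of open-loop and closed-loop stimulation".
- At-home VAS: "364 scores for sham sessions and ~364 scores for active stimulation sessions, per patient".
- Regression: "Multiple regression analysis of all patients will also be used to test for effects of stimulation on various activities, time of day", plus change over the trial and pain etiology.
- The closing sentence compares Phase 1 and Phase 2 VAS scores with Phase 3 VAS scores.

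**Stimulation-off time in Phase 3.** The procedures contain short off/on testing within clinic visits, and an optional wash-out of up to 2 months in item 14 of the Section 1.0 visit list. The matching item 8 in Section 3.0 omits the wash-out.

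**Phase 2.** Sections 1.0 and 3.0, the Protocol Chart and the Nexus System Study text give closed-loop stimulation as the mode compared with none. Section 6.0 says placebo or sham versus open-loop in its Phase 2 text, its cross-phase sentence, its LFP text and its sample size paragraph. Its Phase 2 text also uses the neutral term active stimulation, and the synopsis gives only ON and OFF.

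**The concern.** VAS pain and QST thermal pain threshold are the two primary endpoints in the synopsis. Hypothesis 3 is that closed-loop may outperform open-loop, and Sections 1.0 and 3.0 both say Phase 3 will show which mode works better for each patient. The strategy offered after the trial depends on pain relief during it. If Section 6.0 is followed as written, no analysis contrasts the two randomised modes on either endpoint. The analyst would have to repair the plan with data in hand, including the choice between the off and on QST readings taken at every visit.

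In Phase 2 the sham-controlled contrast is specified, but a reader cannot tell which mode its result describes. Hypothesis 2 concerns open-loop stimulation, so its only possible randomised sham comparison depends on that label.

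**Working it through.** **1. The plan's own counts reproduce.** Inputs are from Section 6.0.

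- Scores per week: 3 × 4 + 2 × 1 = 14.
- Phase 2: 14 × 24 / 2 = 168 per condition, as stated.
- Phase 3: 14 × 52 / 2 = 364 per condition, as stated. 52 / 6 = 8.7 periods, which fits about eight.

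No count error is claimed. The Phase 3 figure uses the whole year as two conditions, which leaves no room for sham alongside both modes.

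**2. Each Phase 3 analysis in Section 6.0.**

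| Analysis | Input as written | Contrasts the modes? |
|---|---|---|
| Per-patient QST t-test | sham vs active periods | No |
| Group analysis | sham vs stimulation scores; both modes named only as its purpose; no method | No |
| At-home VAS comparison | sham vs active sessions | No |
| Regression | stimulation, activity, time, etiology; no mode term named | No |
| Cross-phase VAS | Phases 1 and 2 vs Phase 3 | No; compares phases |

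The count is 0 of 4 within Phase 3, or 0 of 5 with the cross-phase sentence. The mixed models later in Section 6.0 are optional and carry no stated contrast.

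**3. Sham time.** The analysis implies 4 × 6 = 24 weeks of sham per patient. The procedures describe none. One wash-out at its maximum is 2 × 52 / 12 = 8.7 weeks. That is 8.7 / 6 = 1.4 periods, or 8.7 / 24 = 36% of the implied sham time. One wash-out per patient is an assumption; the number is not stated.

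**4. Could sham versus active still be run?**

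- *Taken literally, with four sham periods.* Only four periods remain for two modes. If they split 2 + 2 (an assumption) and all orders are equally likely, an exact permutation test on one patient's periods has a smallest two-sided p of 2/6 = 0.333. With four periods of each mode it is 2/70 = 0.029.
- *Using the off/on QST readings within visits.* Let a and b be the closed-loop and open-loop effects. With equal numbers of visits per mode, the on-minus-off mean estimates (a + b)/2. Illustrative effects (a, b) of (2, 0), (1, 1) and (0, 2) all give 1, while a − b is 2, 0 and −2. This test cannot rank the modes.

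**5. VAS count per mode after relabelling.** All 52 weeks: 364. Four 6-week periods: 4 × 6 × 14 = 336. One full wash-out excluded: (52 − 8.7) × 14 / 2 ≈ 303.

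**6. Phase 2 mode and Hypothesis 2.** If the active mode is closed-loop, there are 0 randomised open-loop versus sham periods in the trial. If it is open-loop, there are 4 versus 4.

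**The case against.** The strongest reply is that this is a labelling slip. The modes are named at the start of the Phase 3 text and again in the sample size paragraph, the VAS count fits exactly two conditions, and the QST and group-analysis sentences repeat the Phase 2 sentences word for word. Sham and active were probably carried over. This stands as an account of the cause, and the intended contrast is recoverable. It does not close the gap: relabelling alone does not say which QST reading is used, where the wash-out sits, or that mode enters the regression. The group analysis naming both modes is weak evidence of a Phase 3 test, because the Phase 2 text says the same.

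A second reply is that this is a 10-patient pilot without a formal sample size, and none of its criteria for a larger trial depends on ranking the modes. That is true. But Hypothesis 3 and the stated purpose of Phase 3 do depend on it, and small size does not excuse a test that differs from the randomised comparison.

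Three narrower points are fair. The cross-phase sentence was never meant as a mode test, so 0 of 4 is the better count. The (a + b)/2 case is one possible fallback, not what Section 6.0 says. And Phase 2 might include both modes, since the Nexus text says the system can deliver either; that is a further reason to reconcile the passages.

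**Conclusion.** The concern holds and should be fixed before analysis. None of the four within-Phase-3 analyses takes closed-loop versus open-loop as its contrast, and the roughly 24 weeks of randomised sham they presuppose appear in no procedure. Hypothesis 3 therefore has no specified test on either primary endpoint, although the intended comparison is clear in general terms. This rests on the current text alone. The wash-out figures assume one wash-out at its maximum, the 2 + 2 split is assumed, and the mode effects are illustrative.

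The Phase 2 conflict is also confirmed. Its effect on Hypothesis 2 is conditional on which mode was meant, and the documents do not settle that.

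**What to change.** In the Phase 3 text of Section 6.0:

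- Replace sham/active with closed-loop/open-loop in the period counts, the QST test, the group-analysis inputs and the VAS counts. Keep about 364 per mode only if all 52 weeks count; otherwise restate it (336 or about 303, as above).
- Define the estimand as the within-patient closed-loop minus open-loop difference over the randomised 6-week periods, for QST and for VAS, and add mode to the regression.
- State which QST reading enters. One option is the stimulation-on reading at the visit that closes each period, which both visit lists place before the mode switch. Another is the on-minus-off change at that visit.
- Name any off versus on QST comparison as a separate, unrandomised contrast.
- Say whether the optional wash-out lies inside or outside the randomisation and how its data are handled, and align the two visit lists.

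Separately, reconcile the Phase 2 active mode between the procedures and Section 6.0, and state which hypothesis each phase tests. This review does not choose the mode. If it is closed-loop, describe Hypothesis 2 as exploratory.

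The cost is relabelling plus a few sentences. The Phase 2 reconciliation may also touch procedure text. No extra patients, visits or data are needed.
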